7.2 General Methodology

All data analyses will be performed by Medtronic or its designee. All statistical analyses will be performed using the Statistical Analysis System (SAS, version 9.4 or higher, SAS Institute Inc. Cary, NC) or other widely accepted statistical or graphical software.

Descriptive statistics will be used to summarize study outcomes. Continuous variables will be summarized using number of subjects (n), mean, standard deviation, median, 25th quartile, 75th quartile, minimum, and maximum. Categorical variables will be summarized using frequencies and percentages.

The study safety and performance analyses related to the procedure and to data through 30 days will occur after all subjects complete the 30-day follow-up visit, discontinued prior to the visit, or were confirmed to miss the visit. A CSR will be prepared once all data collection has ended and all subjects have completed the 30-day follow-up or have exited. A final report will be completed at the end of the 2-year follow-up.

For consideration of study visits, the target number of days from the procedure to each visit is 90 days, 365 days, and 730 days for the 3-month, 1-year, and 2-year visits, respectively.

7.3 Center Pooling

Up to ten study sites will be used. To keep enrollment balanced, a single study site will be allowed to treat no more than 30% of the total population. Study centers will be pooled together for all planned analyses unless they are proven to be heterogeneous in terms of clinical practice, effectiveness and safety.

An assessment of data poolability of the sites will be performed using logistic regression with the outcome being surgery success (1=successful surgery, 0=converted surgery). A p-value of 0.15 or less will be considered significant (per FDA recommendation). Sites with fewer than five treated subjects will be combined into one larger site to ensure statistical robustness. If the sites are found to be significantly heterogeneous with respect to the primary endpoint, additional analyses will be conducted to further assess variations across sites in baseline and procedural variables that might contribute to the variation.

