**Table 6. Professional Competency and Product Training**

	Professional Competency	Product Training
Principal Investigator(s)	
 
• At least 2 years of surgical training and/or experience conducting laparoscopic surgery
 
• At least 2 years robotic experience with the specific study procedure(s) they will be performing for the study
 
• On average, completing 10-12 procedures annually (specifically the study procedure (s) they will be performing for the study)
 
	
 
• Completed simulator exercises on the Medtronic Hugo™ RAS system
 
• Didactic training on the capability and features of the Medtronic Hugo™ RAS system
 
• Completed hands-on training course
 

OR Staff	
 
• At least 2 years of surgical training and/or experience in robotic surgery
 
	
 
• Didactic training on the capability and features of the Medtronic Hugo™ RAS system
 
• Completed hands-on training course
 

All study site personnel will be trained on relevant information prior to their participation in the study.

Surgeon proctoring will be provided to the Investigators as directed by Medtronic Robotic Surgical Technologies. Medtronic personnel may be present for the investigational implants at the sites.

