7.4 Handling of Missing, Unused, and Spurious Data and Dropouts

The primary effectiveness analysis will be based on the FAS. If 5% of the data or fewer are missing for the analysis, no imputation will be used (Buhi, Jakobsen). Otherwise, missing data will be imputed for the FAS using multiple imputation (MI). Unless model errors dictate otherwise, the model variables used for the MI analysis will include baseline variables age, gender (1=female, 0=male), and BMI; the model will also include a variable for hernia cohort (inguinal=1, ventral=0). Ten imputations will be conducted and combined using the Rubin's rule (Rubin) after 100 burn-in iterations. The estimate and variance of the mean proportion of subjects considered a surgical success will be determined for each imputation dataset. For the primary objective, the mean and variance for the proportion will be determined using MI analysis methods and the objective will be tested using a Z-test comparing the observed surgical success rate to the primary objective performance goal of 85%. The seed will be defined as the date of the database snapshot in the format YYYYMMDD.

Sensitivity analysis will be performed for the primary effectiveness objective using available data in both FAS and PPAS as well as tipping-point analysis in FAS to fully understand the missing data impact on the study results.

The primary safety analysis will be based on FAS subjects with available data at 30-days, i.e. whose status (event, no event) at 30-days can be determined. For the secondary and ancillary endpoints, analysis will be conducted with available data in FAS. No imputation will be conducted for these analyses. Additional clarification for determining data availability at 30 days:

- Subjects with a 30-day visit at least 30 days post-procedure have complete/available 30-day data
- For subjects whose 30-day visit occurred within the visit window between 23 and 29 days post-procedure, these subjects will be considered as have been followed through 30 days and their event status will be determined using any events that occurred through 30 days post-procedure, even if occurring after the 30-day visit
- Subjects who did not complete a 30-day visit will be considered to have available data in the following scenarios:
 - 1) if the subject completed zero follow-up visits and has a relevant event in the 30 days following the procedure, the subject will be included in the analysis as having the event;

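### The site-poolability regression has no term for hernia cohort, so a different inguinal/ventral mix between sites can be flagged as site heterogeneity

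*SAP*

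**What the plan says.** SAP 7.3 makes pooling the default: "Study centers will be pooled together for all planned analyses unless they are proven to be heterogeneous", and the sentence goes on to list clinical practice, effectiveness and safety. The one test specified is that "poolability of the sites will be performed using logistic regression with the outcome being surgery success", coded 1 for success and 0 for conversion, with p of 0.15 or less counted as significant. Sites with fewer than five treated subjects are merged. If sites differ, further analyses look at baseline and procedural variables that could explain the variation. CIP 14.10 describes the same regression and follow-up, without the default-pooling sentence. Neither document names a covariate for the model.

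On site composition, SAP 7.3 says "Up to ten study sites will be used" and "a single study site will be allowed to treat no more than 30% of the total population". CIP 9.2 has consecutive enrollment at each institution according to the procedure types needed. CIP Table 6 asks each principal investigator for "At least 2 years robotic experience with the specific study procedure(s) they will be performing for the study", so competency is judged per procedure. I found no rule on the inguinal/ventral mix within a site.

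Elsewhere the plan does use cohort for this same outcome. In the multiple-imputation model of SAP 7.4, "the model will also include a variable for hernia cohort (inguinal=1, ventral=0", next to age, gender and BMI. SAP 7.9.1.7.2 reports effectiveness by cohort.

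**The concern.** A site regression on the combined cohorts asks whether the overall conversion rate differs between sites. That rate depends on how well the site performs within each hernia type and on the share of each type it treats. The purpose of a poolability check is the first. Without a cohort term, the test cannot separate the two.

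Table 6 permits a surgeon who contributes one type only, and the sole site limit is a share of the total: 0.30 × 192 = 57.6, so up to 57 subjects of any mix. An uneven mix is therefore possible. If it occurs and ventral repairs convert more often than inguinal ones, sites that perform identically within type could be reported as heterogeneous. At stake is the meaning of a flag in the study report. It could be read as a difference in site performance, and it could contribute to a finding that centers are heterogeneous, for which SAP 7.3 gives no numerical criterion. The follow-up that might explain it runs only after the flag and does not name hernia cohort.

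**Working it through.** **Figures in the plan.** The documents give no operating figure for the poolability test. The nearest stated figure is the power of the primary effectiveness test (CIP 14.7, SAP 6): 172 subjects, goal 85%, true success 93%, one-sided 0.025. The exact binomial rule is success with at least 156 of 172, attained alpha 0.0189 and power 90.4%, which agrees with the stated 90%. Attrition also reproduces: 172/0.90 = 191.1, rounded up to 192; 86/0.90 = 95.6, rounded up to 96 per cohort. The planning conversion rate is 100% - 93% = 7%.

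**Mechanism.** Let site s treat a share m_s of inguinal subjects, and let conversion be p_I and p_V at every site. The site's expected conversion is m_s·p_I + (1 - m_s)·p_V. Two sites s and t then differ by (m_s - m_t)(p_I - p_V), with no site effect at all. For a 6-point gap (4% and 10%):
- same mix at every site: 0 × 6 = 0 points;
- 80/20 against 20/80: 0.6 × 6 = 3.6 points (5.2% against 8.8%);
- one type per site: 1 × 6 = 6 points.

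**Simulation.** There is no site effect within type, sites are of equal or near-equal size, and a likelihood-ratio test is judged at p ≤ 0.15. The SAP does not say which test of the site term it will use, so the likelihood-ratio test is an assumption. Site only has K - 1 degrees of freedom for K sites. Site given cohort has K - 1, or K - 2 when each site treats one type. Site mix and type-specific rates are assumptions; most pairs average to the planned 7%.

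| Site mix | Conversion, inguinal/ventral | Subjects; sites | Flagged, site only | Flagged, site given cohort |
|---|---|---|---|---|
| One type per site | 7%/7% | 192; 10 or 6 | 23-25% | 23-25% |
| One type per site | 6.15%/7.85% | 192; 10 and 6 | 26% and 25% | 25% and 23% |
| One type per site | 5%/9% | 192; 10 and 6 | 33% and 34% | 24% and 22% |
| One type per site | 4%/10% | 192; 10 and 6 | 45% and 48% | 22% and 20-21% |
| 80/20 | 4%/10% | 192; 10 and 6 | 29% and 31% | 23% and 22% |
| 80/20 | 5%/9% | 172; 10 | 26% | 23% |
| 80/20 | 3%/11% | 172; 10 | 34% | 22% |
| Balanced | 5%/9% | 170; 10 | 23% | 24% |
| Balanced | 3%/11% | 170; 10 | 19% | 22% |

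Monte Carlo error is about 1 point for the 170- and 172-subject rows and for 80/20 at 4%/10%, and smaller for the others. The 1.7-point gap in the second row is 11.1% - 9.4%, the difference between the literature maxima in CIP 6.2.2, centered on 7%. At 9.4%/11.1% themselves, with one type per site, the rates are 25.6% against 25.3% (10 sites) and 21.9% against 20.3% (6 sites).

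**Reading.** The excess needs both an uneven mix and a gap between types. It is large at 4%/10% with one type per site, modest at 80/20 or 5%/9%, and about 1 to 2 points at the literature gap. With equal rates or a balanced mix, leaving out cohort does not raise the flag rate.

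**The case against.** The strongest objection concerns consequence. A reader might infer that a flag stops the pooling of centers or unsettles the primary result. The documents do not support that. The stated action after a significant test is further analysis. Pooling holds "unless they are proven to be heterogeneous in terms of clinical practice, effectiveness and safety", and one effectiveness screen at 0.15 does not cover all three. CIP 14.10 has no clause that ends pooling. The primary effectiveness test remains an exact binomial test on the combined full analysis set (or a Z-test if outcomes are imputed), and no rule replaces it after a flag. This stands in full.

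The second objection is that the plan would reveal a type difference anyway. Hernia type fits within the baseline and procedural variables of the follow-up, effectiveness is reported by cohort regardless, and primary safety is tested by cohort. This stands in part: the explanation is available, but it is not named in advance and comes after the flag.

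The third is that the inputs are hypothetical. Table 6 speaks of one or more procedures and does not describe one-type sites. The literature ranges are similar, both maxima come from the same cited publication, and the sponsor analyzed the types together. This also stands. The pooled 95% prediction interval for conversion, 0.1% to 29.3% (CIP Table 13), does not rule out a larger gap, but it is no evidence of one. Cohort in the imputation model does not show that conversion differs by type either, since age, gender and BMI are there too.

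Finally, it would be too strong to say that the unadjusted test cannot show real site differences. It can detect them; it cannot attribute them. Nor does the fix bring the flag rate down to 15%: both models flag about 23-25% at equal rates because conversions are few (0.07 × 192 = 13.4 expected). That is a separate matter.

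**Conclusion.** The point holds as a conditional weakness in a secondary check. The regression in SAP 7.3 and CIP 14.10 has no cohort term, and nothing in the documents keeps hernia mix similar across sites, so case mix can be flagged as site heterogeneity. With one type per site and no true site effect, omitting cohort raises the flag rate from 20-22% to 45-48% at 4%/10%, from 22-24% to 33-34% at 5%/9%, and by about 1 to 2 points at a 1.7-point gap. It does not raise it when the rates are equal or the mix is balanced. These figures rest on assumed site mixes, assumed type-specific rates and a likelihood-ratio test. The primary effectiveness conclusion and the pooling default are not directly affected; what is affected is the interpretation of a flag. The change is worth making because it costs almost nothing when type is irrelevant and answers the intended question when it is not.

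**What to change.** In SAP 7.3 and CIP 14.10:
- fit surgery success on hernia cohort plus site;
- base the 0.15 assessment on the site term given cohort, stating that where a site treats one type only the comparison is between sites within that type;
- report a site-by-cohort table of subjects and conversions beside the test.

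The cost is one covariate already collected, one sentence in each document and one small table. Enrollment, sample size and the primary analysis do not change.

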7.4 Handling of Missing, Unused, and Spurious Data and Dropouts

The primary effectiveness analysis will be based on the FAS. If 5% of the data or fewer are missing for the analysis, no imputation will be used (Buhi, Jakobsen). Otherwise, missing data will be imputed for the FAS using multiple imputation (MI). Unless model errors dictate otherwise, the model variables used for the MI analysis will include baseline variables age, gender (1=female, 0=male), and BMI; the model will also include a variable for hernia cohort (inguinal=1, ventral=0). Ten imputations will be conducted and combined using the Rubin's rule (Rubin) after 100 burn-in iterations. The estimate and variance of the mean proportion of subjects considered a surgical success will be determined for each imputation dataset. For the primary objective, the mean and variance for the proportion will be determined using MI analysis methods and the objective will be tested using a Z-test comparing the observed surgical success rate to the primary objective performance goal of 85%. The seed will be defined as the date of the database snapshot in the format YYYYMMDD.

Sensitivity analysis will be performed for the primary effectiveness objective using available data in both FAS and PPAS as well as tipping-point analysis in FAS to fully understand the missing data impact on the study results.

The primary safety analysis will be based on FAS subjects with available data at 30-days, i.e. whose status (event, no event) at 30-days can be determined. For the secondary and ancillary endpoints, analysis will be conducted with available data in FAS. No imputation will be conducted for these analyses. Additional clarification for determining data availability at 30 days:

- Subjects with a 30-day visit at least 30 days post-procedure have complete/available 30-day data
- For subjects whose 30-day visit occurred within the visit window between 23 and 29 days post-procedure, these subjects will be considered as have been followed through 30 days and their event status will be determined using any events that occurred through 30 days post-procedure, even if occurring after the 30-day visit
- Subjects who did not complete a 30-day visit will be considered to have available data in the following scenarios:
 - 1) if the subject completed zero follow-up visits and has a relevant event in the 30 days following the procedure, the subject will be included in the analysis as having the event;
 - 2) for subjects without a relevant event and who missed the 30-day visit but had some other post-procedure visit within the 30-day visit window or at anytime after the 30-day window (e.g., a completed 3-month visit), the subject will be included in the analysis as not experiencing the event. Visits and discontinuations after the 3-month visit will not be considered under this provision.

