## 14.4 Primary Objective(s)

### 14.4.1 Primary Objective #1 (Effectiveness)

The primary objectives of this study are to demonstrate that the Medtronic Hugo™ RAS system is safe and effective when used for inguinal and ventral robotic hernia repair. The primary effectiveness endpoint is the surgical success rate, which is defined as the procedure not going into conversion.

The primary effectiveness hypothesis is to test if the surgical success rate is above the performance goal. A performance goal (PG) of 85% (100%-conversion rate) is pre-defined to evaluate the surgical success rate. Let  $P$  be the surgical success rate in this study. The statistical hypothesis is formulated as follows:

$$H_0: P \leq 85\% \text{ vs. } H_a: P > 85\%$$

The hypothesis will be tested using an exact binomial test at one-sided alpha of 0.025. The 95% two-sided confidence interval will also be reported; the confidence interval will be calculated using the Clopper-Pearson exact binomial method.

The analysis set for the primary effectiveness will be the full analysis set (FAS) for the combined inguinal and ventral hernia cohort, which will be further elaborated in **section 14.9**. If 5% of the data or fewer are missing for the primary analysis, no imputation will be used. Otherwise, missing data will be imputed for the FAS using multiple imputation. Sensitivity analysis will be performed for the primary effective

*Medtronic Business Restricted*

endpoint using available data with no imputation in FAS, PPAS as well as tipping-point analysis in FAS to evaluate the robustness of the study results. A summary of device-related conversions will be provided as well.

See **Table 13** below for the rationale supporting the 85% performance goal for the primary effectiveness endpoint. For details on the sample size calculation based on the primary effectiveness endpoint, see details in **Section 14.7**.

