The effectiveness hypothesis is to test if the surgical success rate is above the performance goal. The sample size for primary effectiveness is based on combined cohorts of inguinal and ventral. A performance goal of 85% (100%-conversion rate) is pre-defined to test the statistical hypothesis. Assuming a success rate of 93%, a sample size of 172 subjects for the combined inguinal and ventral hernia cohort will provide 90% of power with one-sided alpha of 0.025. Calculation was performed using the PASS 2023. Accounting for 10% attrition rate, the enrollment is 192 subjects with a hernia repair procedure.

The primary safety objective is also part of the consideration for the sample size determination. The primary safety endpoint is the rate of subjects with any procedure- and/or device-related SSEs from the first incision through 30 days post-procedure. The primary safety objective, assessed separately for each hernia cohort, is based on a performance goal of 30% and expected safety event rate of 15% for the cohort. A sample size of 86 will provide 86% power with a one-sided alpha of 0.0125 (Bonferroni Correction for hernia cohort). Calculation was performed using the PASS 2023. Accounting for 10% attrition rate, the enrollment is 96 per cohort or 192 total subjects with a hernia repair procedure.

An attrition rate of 10% was assumed to ensure an adequate sample for each objective, resulting in 192 total subjects (96 per hernia cohort).

Endpoint	Performance Goal	Expected Study Rate	Minimum Sample Size	Minimum Power	Minimum Alpha
Primary Effectiveness	85%	93%	172	90%	0.025
Primary Safety	30%	15%	86	86%	0.0125

The secondary objectives will be assessed using descriptive statistics and no sample size assessment was made for these objectives.

7. Statistical Methods

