7.5 Adjustments for Multiple Comparisons

For the primary effectiveness endpoint, one hypothesis will be tested at an alpha of 0.025 one-sided. If the one-sided primary objective p-value is <0.025 , then the null hypothesis will be rejected, and the test will be declared statistically significant.

After the primary effectiveness objective is met, the primary safety objective for each hernia cohort will be tested. For the primary safety endpoint (procedure- and/or device-related SSE rate), the closed test procedure (Holm's method, i.e. Holm-Bonferroni method) will be used to protect the overall study-wise error rate for hernia cohorts (inguinal hernia and ventral hernia), thereby maintaining an overall type I error of one-sided of 0.025 for these objectives. To assess statistical significance of these objectives, the one-sided p-values will be determined and ordered from smallest to largest. First, the smaller p-value will be compared to 0.0125. If the p-value is larger than 0.0125, both tests will be considered non-significant. If the smaller p-value is less than 0.0125, the test will be considered significant and the larger p-value will be assessed; the larger p-value is then assessed with a p-value below 0.025 resulting in a determination of statistical significance for the larger p-value.

Secondary objectives and ancillary objectives are intended to be descriptive only. No multiplicity adjustment will be applied.

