7.9.1.5 Analysis Methods

The surgical success rate will be calculated as the proportion of subjects with a successful surgery. The hypothesis will be tested using the binomial test at one-sided alpha of 0.025. In the case of multiple imputation, the objective will be tested using a Z-test. The 95% two-sided confidence interval will also be reported; The confidence interval will be calculated using the Clopper-Pearson exact binomial method, with Wald confidence interval provided in the case of imputation.

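### If more than 5% of conversion outcomes are missing, the Z-test that replaces the exact test for primary effectiveness has a one-sided type I error of about 3.5% to 4.5%, not 2.5%

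*SAP*

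**What the plan says.** Protocol 14.4.1 names one test for primary effectiveness: "The hypothesis will be tested using an exact binomial test at one-sided alpha of 0.025". It is accompanied by a Clopper-Pearson interval. Protocol 14.4.1 and 14.11 call for multiple imputation when more than 5% of the data are missing, with ten imputations combined by Rubin's rule. They do not say which test is applied to the pooled result.

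SAP 7.4 repeats the trigger: "If 5% of the data or fewer are missing for the analysis, no imputation will be used". Above it, the success proportion and its variance are obtained in each imputed dataset and pooled, and "the objective will be tested using a Z-test comparing the observed surgical success rate to the primary objective performance goal of 85" per cent. SAP 7.9.1.5 pairs this with a changed interval, "with Wald confidence interval provided in the case of imputation". The success criterion does not change: under SAP 7.5, "one hypothesis will be tested at an alpha of 0.025 one-sided", and SAP 7.9.1.3 still requires p below 0.025.

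SAP 7.9.1.7.1 makes the same imputation analysis the first sensitivity analysis when the primary analysis uses no imputation.

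**The concern.** The SAP does not call the test a Wald test. But a variance determined within each imputed dataset is not the null variance, and the interval that goes with it is named as Wald. At about 90% success, p(1 − p) is 0.09, while under the null of 85% it is 0.1275. The standard error is therefore too small in just the region where the test is decided, and Z is too large.

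This single-arm study rests its effectiveness claim on this one test, and under SAP 7.5 the two safety tests follow only if it succeeds. The missing-data rule should not relax the error rate. As written, moving from at most 5% missing to just above it exchanges a conservative test for a liberal one at the same nominal level. Where some outcomes are missing but no more than 5%, the planned robustness check is also easier to pass than the primary test it is meant to support.

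**Working it through.** **Inputs.** Null rate 85%, assumed rate 93%, n = 172, enrolment 192 (SAP section 6); one-sided alpha 0.025 (SAP 7.5); ten imputations, Rubin's rule, trigger above 5% missing (SAP 7.4).

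**1. The plan's own figure.** SAP section 6 says: "Assuming a success rate of 93%, a sample size of 172 subjects for the combined inguinal and ventral hernia cohort will provide 90% of power". The exact binomial test at n = 172 rejects from 156 successes. Its true size is 1.89% and its power at 93% is 90.4%, so the stated 90% reproduces. Attrition also reproduces: 172/0.90 = 191.1, rounded up to 192.

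**2. Complete data: estimated variance against the exact test.** The estimated-variance rule rejects when

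Z = (p̂ − 0.85) / √(p̂(1 − p̂)/n) > 1.960.

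Take 172 successes in 192, so p̂ = 0.8958:
- Estimated standard error: √(0.8958 × 0.1042/192) = 0.0220. Z = 0.0458/0.0220 = 2.08, which rejects.
- Null standard error: √(0.85 × 0.15/192) = 0.0258. Z = 0.0458/0.0258 = 1.78, which does not reject.
- Exact tail probability P(X ≥ 172) at 85%: 4.19%, which does not reject.

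| n | Exact: rejects from | Exact size | Estimated-variance Z: rejects from | Size |
|---|---|---|---|---|
| 172 | 156 | 1.89% | 155 | 3.31% |
| 182 | 165 | 1.67% | 163 | 4.78% |
| 192 | 174 | 1.47% | 172 | 4.19% |

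Because counts are discrete, the size moves with n. Over n = 172 to 192 the Z rule averages 4.20% (range 3.30% to 5.14%), while the exact test never exceeds 2.4%. At N = 192, results of 172 and 173 successes fail the exact test and pass the Z rule.

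**3. The imputation branch as written.** The pooled variance is Rubin's total, T = W + (1 + 1/10)B, where W is the mean of p̂(1 − p̂)/n over the ten datasets and B is the between-imputation variance. Simulated size at a true rate of 85%, missing completely at random:
- Beta-posterior imputation without covariates, 5% to 15% missing, N = 172, 182 and 192 (200,000 runs per setting): 4.1% to 4.4%.
- Logistic imputation with four covariates unrelated to outcome, 6% and 10% missing, N = 172 and 192 (20,000 runs per setting): 3.6% to 3.9%.

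The between-imputation term does not remove the excess. Neither does a t reference in place of the normal: at N = 192 with 10% missing, 4.12% against 4.15%.

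**4. Same branch with the null variance.** Replacing W by 0.85 × 0.15/n and keeping (1 + 1/10)B gives a simulated size of about 2.1% to 2.3%.

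**The case against.** The strongest reply is that the branch is remote. Protocol Table 7 collects conversion only at the surgical visit, SAP 7.9.1.2 derives it from the site's report of the procedure, and the full analysis set contains only subjects with a first incision. The 10% attrition allowance is mostly a matter of 30-day follow-up and should barely touch this outcome. Reaching the trigger at N = 192 takes 10 missing outcomes (10/192 = 5.2%). That stands, and it makes this a conditional defect.

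Second, safeguards exist. When imputation is used, the first sensitivity analysis takes available cases, to which the binomial test applies, and a tipping-point analysis treats missing outcomes as failures (SAP 7.9.1.7.1). These would show a pass that depended on the Z-test, but they do not alter the primary decision rule. Likewise, using the Z-test as a sensitivity analysis spends no confirmatory alpha; there it only makes the check too lenient.

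Third, the protocol leaves technical detail to the SAP, and an exact test cannot be applied directly to pooled imputed data, so some pooled test was needed. That also stands. The fault is in the variance chosen, not in having a Z-test.

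A reader might infer that ever more missing data makes the trial ever easier to pass. The plan does not have that property. There is one jump at the 5% switch: at N = 192 and 93% success, power is 91.9% for the exact test on complete data and about 96% under imputation with 5.5% missing. Beyond the switch, power falls to about 95% at 10% missing and 94% at 15%, while size hardly moves.

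**Conclusion.** In the branch with more than 5% of conversion outcomes missing, the primary effectiveness test does not hold its stated one-sided 0.025. Its size is about 3.5% to 4.5%, against about 1.5% to 1.9% for the exact test on complete data at the planned sample sizes. Error control is lost on crossing the threshold.

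Two broader readings are not supported. The trial's overall type I error is not 4%: the excess is conditional on a branch that is unlikely to be entered, and the default exact test is conservative. Nor is a single figure such as 4.2% settled, since it depends on the number of subjects and the imputation model.

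The result rests on reading the SAP's variance as the estimated one, which its text and the Wald interval support, and on simulations with data missing completely at random. The change is worth making before the database snapshot, as a conditional correction and not as a flaw in the main test.

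**What to change.** Keep multiple imputation, as the protocol requires, and edit SAP 7.4 and 7.9.1.5 only:
- Test with Z = (p̄ − 0.85)/√(0.85 × 0.15/n + (1 + 1/10)B), where p̄ is the pooled proportion and B the between-imputation variance.
- Replace the Wald interval with the matching score-type interval: all values p for which |p̄ − p| ≤ 1.960 × √(p(1 − p)/n + (1 + 1/10)B).
- The first sensitivity analysis in SAP 7.9.1.7.1 refers back to 7.4 and so follows automatically.

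The cost is some power relative to the Z-test as written. At 93% success and N = 192 it is about 92% instead of 96% with 5.5% missing, and 91% instead of 95% with 10% missing, so still above the planned 90%. The rule remains a normal approximation: with complete data at N = 192 its size would be 2.55%, but with the between-imputation term the simulated size is below 2.5%. Enrolment and data collection do not change.

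Do not make missing-as-failure the primary rule. At N = 192 the exact test needs 174 successes. With 10 outcomes missing and counted as failures, power at 93% success falls from 91.9% to about 10%. It would also replace the imputation written into the protocol and so need an amendment. It belongs where the SAP already has it, in the tipping-point analysis.
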